## 4. STUDY DESIGN

This is a multi-centre validation comparison study comparing pathologists' diagnoses using digital whole slide imaging (DP) with their diagnoses using glass slide light microscopy (LM), the current standard practice within the NHS. The order in which the pathologists view the images (DP and LM) will be randomised.

To achieve objectivity, we have introduced a washout period of a minimum of six weeks between the two viewings (LM and DP) of the same sample by the same pathologist.

An integrated pilot study will test the working practices and processes of the study for any unforeseen problems. It also aims to assess whether it is feasible to include at least 10% difficult cases and 10% moderate cases for the skin, GI and breast specialties. The results of this study will be reviewed by the Study Steering Committee.

## 5. AIMS AND OBJECTIVES

#### Pilot study objectives

- Assess the ability of different sites to identify appropriate samples in time and on target
- Examine the intricacies involved in selecting samples and forwarding the appropriate glass slides to Coventry coordinating centre for scanning, as well as observe the rotation of sample case sets between sites following each pathologist's review (site/pathologist)
- Assess access to the digital slides on the central server by pathology investigators, and ability to view and report them appropriately
- Assess access and functionality of Warwick CTU database system (web application)
- Eye tracking of the pathologists will be carried out to ensure that there are no local unforeseen technical difficulties with the approach prior to the main study, and to familiarise study pathologists with the technique
- Identify potential barriers to the adoption of DP and explore the experiences and views of pathology staff migrating from LM to DP by means of focus groups and semi-structured telephone interviews

#### Main study primary objective

The primary objective of this study is to compare pathologists' diagnoses made by assessment of LM of breast, GI, skin and renal samples, with the same pathologists' diagnoses of the same samples (intra-rater reliability) using DP.

#### Main study secondary objectives

- Compare DP to LM in reporting histopathology slides to measure variation between pathologists on both modalities (inter-rater reliability)
- Explore the likely costs and benefits associated with DP compared with LM using a Health Economic evaluation

- Explore the existing views of the pathology staff (pathologists and technicians) and the impact of introducing DP (migration from LM to DP) on pathologists and laboratory workforce with a view to understanding the barriers and facilitators to DP
- Determine how the study pathologists examine DP images of different pathology modalities to establish how the techniques used to examine these images contribute to error in their interpretation

## 6. OUTCOME MEASURES

#### Primary outcome measure

Level of agreement between each pathologist's DP and LM diagnoses (intra-pathologist)

#### Secondary outcome measures

- Inter-pathologist level of agreement across the four DP diagnoses and the ground truth (GT)
- Inter-pathologist level of agreement across the four LM diagnoses and the GT
- Individual pathologists' non-concordance rates over the course of the study, and clinical relevance of these non-concordances, including treatment decision-making and cost analysis of error
- Measurement of the productivity of pathologists using DP in comparison to LM, the contribution of DP to reducing error and the cost and benefits associated with avoiding significant errors
- Qualitative assessment of barriers and facilitators to DP, and experiences and views of pathologists and laboratory staff using DP
- Pathologist observer error (visual perceptual and cognitive) using eye tracking software

## 7. SAMPLE PATHWAY

## 7.1 Sample selection criteria

Histopathology samples from five participating NHS trusts will be selected. All samples are collected for the purpose of routine histopathology reporting and only entered into the study on completion of their clinical review at the respective NHS participating site.

There are four sub-specialty areas that are included in the study: breast, gastrointestinal (GI), skin and renal. The sample selection process will be devised to include cancer screening biopsies and will be enriched (20%) for areas of difficulty, with the exception of renal samples where all are considered difficult cases:

- Breast (Belfast, Coventry, Lincoln & Nottingham): A total of 600 samples including at least 200 cancer screening biopsies enriched with:
  - o At least 10% resected tumours (moderately difficult)
  - 10% difficult samples: low grade ductal carcinoma in situ, atypical hyperplasia, screening category B3 and B4, lesions with calcium oxalate (Weddellite calcification), sclerosing and papillary lesions, and micrometastases
- GI (Coventry, Belfast & Nottingham): A total of 600 samples including at least 200 cancer screening biopsies enriched with:
  - At least 10% resected tumours (moderately difficult)
  - 10% difficult: oesophageal dysplasia, polyp cancers, inflammatory bowel disease, minimal change colitis, graft versus host disease, giardiasis, cytomegalovirus, H. pylori and herpes virus infection
- Skin (Coventry, Belfast & Lincoln): A total of 600 samples enriched with:
  - o At least 10% non-basal cell carcinoma cancer resections (moderately difficult)
  - 10% difficult: sentinel nodes, dysplastic naevi, spitz naevi, lentigo maligna, early and desmoplastic melanoma, herpes virus infection, leischmaniasis, leprosy, amyloid, angioscaroma, and Kaposis sarcoma
- Renal (Oxford only): A total of 200 sequential native biopsies for glomerular, tubulointerstitial and vascular disease and transplant biopsies for graft rejection. No enrichment is planned in the renal biopsy group as all of these biopsies are difficult to report.

**Please note: Difficult cases might have more diagnostic entities than listed above.** All cases will be accompanied with a pseudonymised histopathology report. Samples with either broken or missing slides, or with missing clinical data, will not be considered; neither will megablocks or oversized slide sets. Cases where a prior sample is important to the interpretation of the study sample should also be excluded.

## 7.2 Inclusion into the study

Warwick Clinical Trials Unit will provide a bespoke online sample tracking database. Site staff will be able to access this from their workplace to enrol samples. Individual log in details (usernames and passwords) will be provided.

## 7.2.1 Samples from Belfast, Nottingham and Lincoln (breast, GI and skin)

The pathologist at site will identify each sample for the study following its routine diagnosis and pass it to their technicians for processing and shipping to Coventry coordinating centre. Upon receipt of the sample from the pathologist, the technician will need to:

- Enrol each sample on the Warwick Clinical Trials Unit (WCTU) database system. Sample details including non-identifiable patient details, sample difficulty level, number of parts/blocks/slides, reference diagnosis etc will need to be provided as part of the enrolment process.
- Pseudonymise the slides and associated histopathology report(s) by redacting all patient identifiable information leaving only the histology number visible. This will enable the samples to be returned to their original site once the study has been completed. The pseudonymised histopathology report(s) will need to be provided during the enrolment process, either as a file upload or as free text.
- Log the sample(s) as being sent to Coventry coordinating centre, as per local SOP and on the WCTU database system. The database will alert the coordinating centre about this forthcoming shipment.
- Send the sample(s) to Coventry coordinating centre

When the samples are received by Coventry coordinating centre, each sample will be checked for quality control (for example that slides are in good condition) prior to being scanned onto the IMS. If all criteria are met, the sample will be allocated a unique 'study number' generated by the database system. The study number certifies the sample as fully anonymised. This study number, along with other details, will be barcoded by trained coordinating staff using the current UHCW process, and the barcode will be placed on the slides. Following this, the slides will be immediately digitised.

If the sample selection criteria are not met, the case is declined. The sample is marked as ineligible on the WCTU database then returned to the originating site. Return of the sample is tracked on the WCTU database.

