## 7.2.3 Samples from Oxford (renal)

Renal samples will be enrolled from Oxford only. Pathologists identify the sample(s) for the study and pass to their technicians. Technicians then need to:

- Enrol each sample on the WCTU database system. Sample details including non-identifiable patient details, number of parts/blocks/slides, reference diagnosis etc will need to be provided as part of the enrolment process.
- Pseudonymise the histopathology report(s) by redacting all patient identifiable information leaving only the histology number visible. The pseudonymised histopathology report(s) will need to be provided during the enrolment process, either as a file upload or as free text.
- The WCTU database system will produce a unique anonymised study number for each enrolled sample.

- Label the sample slides with the study number. If applicable, immunofluorescence (IF) stained slides of the original image will be anonymised with the same study number and used for the study.
- Digitise the slides
- Log the sample(s) as being sent to Coventry coordinating centre, as per the existing local laboratory SOP and on the WCTU database system, using the unique study number in the record. The database will alert the coordinating centre about this forthcoming shipment.
- Send the sample(s) to Coventry coordinating centre

Quality control and eligibility checks of renal samples at Coventry coordinating centre will follow the same process as for breast, GI and skin.

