## 7.6 Distribution and tracking of samples following enrolment, batching and randomisation

Following batching and randomisation, the two pathologists in the 'DP first' group will be assigned the digital images. These pathologists will view the samples on the Philips Image Management System (IMS) and report their findings using WCTU database system's electronic Case Report Form (eCRF). Once one of these pathologists has completed the reporting of the entire batch, the system will prompt the technicians at Coventry coordinating centre to package up the glass slides and dispatch to the first pathologist in the 'LM first' group.

As and when a site receives a batch of glass slides, the technician (or other trained staff member) should record the received date on the WCTU database system and check the condition of the slides, then pass them on to the pathologist for viewing and reporting.

Once the first pathologist in the 'LM first' group has completed reporting, the system will prompt the pathologist to pass the slides back to the technician(s). The technician(s) will then send the glass slides to the site at which the second pathologist in the 'LM first' group is based.

For each of the pathologists, a 6 week washout period begins from the date on which their first read is completed.

For the second reads, the glass slides will be made available to the pathologists in the 'DP first' group (one followed by the other, in a fixed order, and only when each pathologist's 6 week washout period has ended). The glass slides will then be returned to Coventry coordinating centre.

When 6 weeks have passed since the completion of the 'LM first' pathologists' first reads, the WCTU database system will prompt the technicians at Coventry coordinating centre to assign the digital images to the 'LM first' pathologists.

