## 9. INFORMED CONSENT

The study involves use of previously collected tissue for routine pathology assessment. All samples will be anonymised and returned to the site once all diagnoses have been completed. Therefore, no patient consent is required.

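### Breast, GI and skin slides are prepared with the source laboratory's histology number visible; the protocol does not say it is hidden before slides reach readers, yet calls these linkable samples fully anonymised

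*Protocol*

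**What the plan says.** Protocol section 7.2.1 covers Belfast, Nottingham and Lincoln. The technician's instruction is "Pseudonymise the slides and associated histopathology report(s) by redacting all patient identifiable information leaving only the histology number visible". The reason given is "This will enable the samples to be returned to their original site once the study has been completed". The report goes onto the trials unit database as well: "The pseudonymised histopathology report(s) will need to be provided during the enrolment process, either as a file upload or as free text".

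After quality control at Coventry, the same database issues a study number. It is printed as a barcode and "the barcode will be placed on the slides", and the slides are then scanned. Of the study number, the section says "The study number certifies the sample as fully anonymised".

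Section 7.2.2 applies a similar process to Coventry's own cases and gives its purpose as keeping them unidentifiable to the Coventry research team.

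Section 7.2.3 (renal, Oxford) differs. Only the report is said to keep the histology number. For the glass, the instruction is "Label the sample slides with the study number".

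Section 7.6 sends the glass from reader to reader, for example "The technician(s) will then send the glass slides to the site at which the second pathologist in the 'LM first' group is based". Section 7.5 requires readers to be blind to the reference diagnosis. Section 9 notes that the tissue was already collected for routine assessment and continues: "All samples will be anonymised and returned to the site once all diagnoses have been completed. Therefore, no patient consent is required".

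**The concern.** Two separate things are at stake.

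**Blinding.** The histology number is the source laboratory's own key to the case. To an outsider it identifies nobody. To a reader employed at that laboratory, it could lead to the report already issued, which is the reference diagnosis. The primary outcome is agreement between the same reader's DP and LM diagnoses, so the two reads need to be independent of that report. Barring readers from cases they reported themselves would not close this route, because colleagues at the same laboratory could still use the number.

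**Stated status.** A sample that carries, or is linked in a database to, its laboratory number is pseudonymised. The protocol uses that word for the preparation step, then describes the same sample as fully anonymised, and section 9 draws its no-consent conclusion partly from anonymisation. The described procedure does not deliver the property that is claimed.

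**Working it through.** The protocol gives no figure on this point to reproduce. The check compares passages and adds one count.

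**1. Is the number hidden before circulation?** The steps in section 7.2.1, in order, are: redact all but the histology number; ship to Coventry; quality control; study number issued; barcode applied; scan. No step removes or covers the histology number. Its stated use comes after the study ends, so on the plain reading it has to survive both reads. Section 7.2.2 shows that relabelling is meant to conceal identity, but gives no instruction that achieves this. Visibility to readers is therefore a reasonable inference from the text, not something the text states.

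**2. Who could make use of it?** Supplying sites come from section 7.1 and readers per site from the table in section 7.4. The reader counts sum to four per specialty, as the protocol says they should.

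| Specialty | Supplying sites (readers at each) | Readers at a supplying site |
|---|---|---|
| GI | Coventry (1), Belfast (2), Nottingham (1) | 4 of 4 |
| Skin | Coventry (2), Belfast (1), Lincoln (1) | 4 of 4 |
| Breast | Belfast (1), Coventry (0), Lincoln (1), Nottingham (2) | 4 of 4 |

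That is 12 of 12 readers. Each specialty has 600 samples × 4 readers = 2,400 reader-sample pairs, so 7,200 in all.

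**3. How many pairs are read at the source laboratory?** For each specialty, sum over sites (samples supplied × readers at that site). Site contributions are not given, so equal shares are assumed:

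- GI: 200 × (1 + 2 + 1) = 800 of 2,400 (33.3%)
- Skin: 200 × (2 + 1 + 1) = 800 of 2,400 (33.3%)
- Breast: 150 × (1 + 0 + 1 + 2) = 600 of 2,400 (25%)
- Total: 800 + 800 + 600 = 2,200; 2,200 / 7,200 = 30.6%

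The arithmetic limits, with each specialty supplied by a single site, are:

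- Lowest: GI 600 × 1, skin 600 × 1, breast 600 × 0 = 1,200 (16.7%)
- Highest: 600 × 2 in each = 3,600 (50%)

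Section 7.1 names several sites per specialty, so neither limit is realistic. Every pair includes one LM read, at which the reader has the glass itself.

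**4. Are the samples linkable?** Yes, on three grounds:

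- The report bearing the histology number is entered on the database that issues the study number (7.2.1).
- Samples go back to their site (7.2.1 and 9).
- The steering committee may act case by case on clinically important differences between ground truth and reference diagnosis (18.5), which appears to need a link.

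**5. Effect on agreement.** This would need the share of pairs in which a report was looked up, and at which read. The documents give neither. Look-up at both reads would pull them together. Look-up at only one could pull them apart.

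**The case against.** The best defence is that the visible number is stated only for preparation and shipment. Coventry then relabels under its existing hospital process, and that label may well cover the old number. Section 7.2.2 supports this, since relabelling is meant to hide identity from the source laboratory itself. This stands as far as it goes: a reader might infer that slides are known to circulate with the number showing, and the protocol does not say so. But the instruction to leave the number visible is explicit, and the step that would hide it is not.

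Second, a reader would have to search the laboratory system in breach of section 7.5. That is fair, and nothing suggests that anyone would. Blinding is nevertheless better secured by labelling than by trust when the label costs almost nothing.

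Third, renal slides do not fit. Section 7.2.3 leaves the number on reports only and labels the slides with the study number. This stands, so renal pairs are left out of the count and the point does not extend to every case. Section 7.2.3 is merely silent on what happens to any original label.

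Fourth, section 9 also relies on the tissue being already collected, section 18.2 records HRA and REC approval, and section 16 records that the lack of consent was discussed with public members. A reader might infer that the approval without consent fails. The documents do not support that: they cannot show what the committee was told or what it requires for linked samples.

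**Conclusion.** The concern holds in a limited form. For breast, GI and skin, the protocol keeps the source laboratory's number visible by design, adds a barcode without saying that it hides the number, and circulates the glass to readers who all work at a supplying site for their specialty. About 2,200 of 7,200 pairs (30.6%) would be read at the source laboratory. This assumes equal site contributions and takes the reader table as printed. It counts pairs where the route could exist if the number stayed visible, not pairs affected.

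It is tempting to turn this into a stated upward shift in DP-LM agreement. The documents supply no look-up rate and do not fix the direction, so neither a size nor a sign can be given.

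The wording conflict holds without any assumption. Linked samples are called pseudonymised and then fully anonymised, and section 9 uses the latter idea in its no-consent statement. These passages must be reconciled. That is a correction to the text, not a finding that approval is invalid.

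**What to change.** - **Sections 7.2.1 and 7.2.2:** require the study label to cover the histology number and any original label before scanning and dispatch, with a check that the number does not show in the scanned label image.
- **Section 7.2.3:** state the same for any original label on renal slides.
- **Link:** hold the correspondence between study number and histology number only in the trials unit database, and use it to return slides. That database already tracks the return of declined samples.
- **Sections 7.2.1 and 9:** replace the anonymisation wording with wording that fits linked, pseudonymised samples, and confirm that the approval without consent covers them.

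The cost is a change of label placement, a database field, a few words in an amendment and a database look-up when slides are returned. No extra samples or staff are needed.

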## 7.2.2 Samples from Coventry (breast, GI and skin)

A similar process as above will be followed for samples identified from Coventry site, including the allocation of study numbers and barcode labelling, so that these samples are not identifiable to the research team at Coventry.

## 7.2.3 Samples from Oxford (renal)

Renal samples will be enrolled from Oxford only. Pathologists identify the sample(s) for the study and pass to their technicians. Technicians then need to:

- Enrol each sample on the WCTU database system. Sample details including non-identifiable patient details, number of parts/blocks/slides, reference diagnosis etc will need to be provided as part of the enrolment process.
- Pseudonymise the histopathology report(s) by redacting all patient identifiable information leaving only the histology number visible. The pseudonymised histopathology report(s) will need to be provided during the enrolment process, either as a file upload or as free text.
- The WCTU database system will produce a unique anonymised study number for each enrolled sample.

- Label the sample slides with the study number. If applicable, immunofluorescence (IF) stained slides of the original image will be anonymised with the same study number and used for the study.
- Digitise the slides
- Log the sample(s) as being sent to Coventry coordinating centre, as per the existing local laboratory SOP and on the WCTU database system, using the unique study number in the record. The database will alert the coordinating centre about this forthcoming shipment.
- Send the sample(s) to Coventry coordinating centre

Quality control and eligibility checks of renal samples at Coventry coordinating centre will follow the same process as for breast, GI and skin.

## 7.3 Batch process and randomisation

When enough samples per specialty have been received by the coordinating centre, the coordinating centre will batch the samples using the WCTU database system.

The system will allocate a unique batch number and then randomise the batch by selecting which group of pathologists will view using light microscopy (LM) first and which will view using digital pathology (DP) first.

## 7.4 Reporting pathologists

Six NHS histopathology laboratories (Coventry, Belfast, Lincoln, Oxford, Nottingham, Birmingham) will each have specialist pathologists to report on relevant disease areas. In each area, four pathologists will report the same series of samples twice, once each with LM and DP, thereby allowing comparison within and between observers over both platforms.

Centre/disease specialty	GI	Skin	Breast	Renal
Coventry	[name]	[name] [name]		[name]
Belfast	[name] [name]	[name]	[name]	
Lincoln		[name]	[name]	
Nottingham	[name]		[name] [name]	
Oxford				[name] [name]
Birmingham				[name]

Specialist reporting pathologists at each centre by specialty are shown below:
--

The estimated time to make these readings based on current work-diary exercise data is one 4 hour session per week over 24 months.

